5. AGENT ADMINISTRATION

Intervention will be administered on an outpatient basis. Reported adverse events (AEs) and potential risks are described in Section 6.2.

5.1 Dose Regimen and Dose Groups

Eighty participants with liver cirrhosis will be randomized into one of 2 groups: 40 participants will receive 40 mg simvastatin per day and 40 participants will receive a placebo identical in color, consistency, and appearance to simvastatin 40 mg. Simvastatin and placebo will be provided as over-encapsulated tablets. Dosing will extend for 6 months.

- Agent(s): Simvastatin and placebo
- Daily dose(s) and regimen(s) for each agent: One 40 mg capsule per day
- Duration for each agent: Daily treatment for 6 months

The usual recommended dose of simvastatin is 10-40 mg/day, and the toxicity and tolerability are comparable for 20 mg and 40 mg [23]. In a prior published trial of patients with chronic hepatitis or cirrhosis, statin dosing began at 20 mg and was titrated up to 40 mg, and no serious side effects or discontinuation of therapy were noted [56]. Thus, we feel that a 40 mg dose will be well-tolerated by the participants in this trial.

5.2 Study Agent Administration

Patients will self-administer the 40 mg capsule of simvastatin or placebo daily in the evening. Patients will be instructed to take the study agent at bedtime or with an evening meal. Each participant will be given/shipped one bottle of 120 capsules at Study Visit 1 (90-day supply + buffer) and one bottle of 120 capsules (90-day supply + buffer) at Study Visit 3 (Month 3).

5.3 Run-in Procedures

None.

5.4 Contraindications

Patients are advised not to consume any form of grapefruit (e.g., juice, fruit, grapefruit seed extract, dietary supplements containing grapefruit) while on simvastatin as grapefruit may increase the blood levels of simvastatin [114]. Participants enrolled in the study will be instructed to avoid all forms of grapefruit.

The combined use of simvastatin with systemic formulations of gemfibrozil, cyclosporine, danazol, lomitapide, verapamil, diltiazem, dronedarone, amiodarone, amlodipine, ranolazine, or strong CYP3A4 inhibitors (e.g., itraconazole, ketoconazole, posaconazole, voriconazole, HIV protease inhibitors, boceprevir, telaprevir, erythromycin, clarithromycin, telithromycin, nefazodone, and cobicistat-containing products) is contraindicated due to an increased risk for myopathy. Patients will be screened for contraindications to simvastatin prior to enrollment in the study. Patients with known active infection with HIV will be excluded from the study. Patients will be advised not to use contraindicated medications during the study and will be reviewed at study visits and during follow-up telephone calls. Participants will be closely monitored for symptoms and side effects to the study drug and will be instructed to call the study doctor immediately if they have a serious adverse reaction.

5.5 Concomitant Medications

All medications (prescription and over-the-counter), vitamin and mineral supplements, and/or herbs taken by the participant will be documented on the concomitant medication CRF and will include: 1) start and stop date, dose and route of administration, and indication. Medications taken for a procedure (*e.g.*, biopsy) should also be included.

5.6 Dose Modification

No dose modifications are planned. The study agent will be stopped in the event of an AE \geq grade 3 considered possibly, probably, or definitely related to the study agent. The study agent will be restarted after resolution. One of the common side effects of statin medication is myalgia (muscle pain with normal Creatine Phosphokinase (CPK) level), and rarely this is associated with statin myopathy (muscle weakness or other muscle injury with or without elevation in CPK level). In randomized controlled trials of standard dose statin therapy, the risk is very low (<1%). We will measure levels of CPK in the blood drawn at the first study visit to establish a patient-specific reference for this indicator of muscle toxicity. During the trial, if the participant reports unexplained muscle pain or weakness, CPK will be tested again to check for elevation.

The study agent will be permanently discontinued in subjects experiencing grade 3 or greater myopathy (unexplained muscle symptoms *and* CPK > 5 times ULN) or hepatotoxicity (ALT or AST > 5 times

ULN) that is considered possibly, probably, or definitely related to the study agent. The study agent will be permanently discontinued in subjects experiencing the following grade 2 hepatotoxicities considered possibly, probably, or definitely related to the study agent: (1) hemorrhage requiring medical attention, and (2) symptomatic fistulas. All other grade 2 hepatotoxicities can be restarted after resolution.

Because dose modification could lead to lack of dose homogeneity that may impair the research objectives, we will stop the intervention in patients who initiate drugs that require dose modifications of simvastatin below 40 mg: lomitapide, verapamil, diltiazem, dronedarone, amiodarone, amlodipine, or ranolazine.

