8.3 Off-Agent Criteria

Participants may stop taking study agent for the following reasons: completed the protocol-prescribed intervention, AE or serious adverse event (SAE), inadequate agent supply, noncompliance, concomitant medications, or medical contraindication. See Section 5.6. Dose Modification for additional off-agent criteria. Participants will continue to be followed, if possible, for safety reasons and in order to collect endpoint data according to the schedule of events.

As described in section 7.5, clinical research staff will make follow-up telephone calls to the participant on days 30 ± 7 , 60 ± 7 , and 90 ± 7 after the participant discontinues the study agent to assess symptoms and adverse events. Standard of care data (medical history, concomitant medications, laboratory test results, imaging results) will continue to be collected via review of the participant's electronic medical record at the time points specified in the Schedule of Events. If feasible, we will conduct a research visit to collect final measurements for participants who permanently discontinue the study agent early. An endof-study research visit will be conducted 6 months (\pm 30 days) after initiation of the statin intervention (Study Visit 4). The procedures that will be performed during the end-of-study visit are described in section 7.4.1 Study Visit 4.

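### Section 5.6 requires a permanent stop for related hemorrhage and fistulas at grade 2 only; read literally, the same events at grade 3–4 lead to a restart

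*Combined protocol and SAP*

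**What the plan says.** Section 5.6 gives four instructions, all for events judged at least possibly related to the agent:

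1. **Any adverse event of grade 3 or higher.** The agent is stopped, and then "The study agent will be restarted after resolution". The sentence carries no exception and no upper grade limit.
2. **Grade 3 or greater myopathy or hepatotoxicity.** The agent is stopped permanently. Each term has a bracket after it. Myopathy is muscle symptoms together with CPK above 5 times ULN. The other term reads "or hepatotoxicity (ALT or AST > 5 times" ULN.
3. **Two named events at grade 2.** "The study agent will be permanently discontinued in subjects experiencing the following grade 2 hepatotoxicities considered" at least possibly related, namely ("1) hemorrhage requiring medical attention, and (2) symptomatic fistulas".
4. **The rest of grade 2.** "All other grade 2 hepatotoxicities can be restarted after resolution".

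Section 8.3 (Off-Agent Criteria) lists reasons for which a participant may stop the agent, among them "AE or serious adverse event (SAE), inadequate agent supply, noncompliance, concomitant medications, or medical contraindication". It then points back: "See Section 5.6. Dose Modification for additional off-agent criteria".

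**The concern.** The third rule omits the words *or greater*, which the second rule includes. A site that follows the text would stop the agent for good after a grade 2 hemorrhage, yet plan to restart it after a grade 3 or 4 hemorrhage has resolved. Under the severity scale in Section 11.1.3, grade 3 is the level at which hospital admission is indicated and grade 4 is life-threatening, so the instruction becomes more lenient as the event gets worse.

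What is at stake is participant safety, not inference. The population makes bleeding a realistic event: all participants have cirrhosis, platelets as low as 50,000/microliter are eligible (Section 4.1.4), and varices are among the sequelae assessed at Screen 1 and Study Visit 4. The attribution threshold is also low, since a possible relation is enough to bring the rules into play.

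**Working it through.** The documents contain no figure to reproduce here. The check applies the four rules of Section 5.6 to each case, for a related hemorrhage requiring medical attention or a related symptomatic fistula.

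| Case | Rule 2 (grade ≥3, ALT/AST >5× ULN) | Rule 3 (named events, grade 2) | Rule 1 (any AE, grade ≥3) | Literal outcome |
|---|---|---|---|---|
| Grade 2 | not met (grade) | met | not met | permanent stop |
| Grade 3–4, with related ALT/AST >5× ULN | met | not met (grade) | met | permanent stop |
| Grade 3–4, without related ALT/AST >5× ULN | not met (bracket) | not met (grade) | met | stop, then restart after resolution |

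Stated permanent-stop coverage of the two event types:

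- grade 2: 2 of 2
- grade 3–4 without related ALT/AST >5× ULN: 0 of 2

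The next step is whether any other section supplies the missing rule.

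- **Section 8.3** is permissive (participants *may* stop) and refers back to Section 5.6.
- **Section 8.4** lists an adverse event and a physician's decision as possible reasons for going off study. It does not govern restart.
- **Section 8.5** is a study-level accrual stop, triggered when 30% or more of participants come off agent for serious events probably or definitely related to it. It is not a rule for the individual participant.
- **Sections 11.2 and 12.4** set notification, follow-up and committee review. Neither states a restart decision.

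None of these closes the third row of the table. The documents give no rate for either event, so no number of affected participants can be derived.

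**The case against.** The strongest counter-reading is that Section 5.6 is tiered. Its third rule itself calls hemorrhage and fistulas hepatotoxicities, although neither is a transaminase value. If the word keeps one meaning across adjacent sentences, grade 3 or greater hepatotoxicity already includes these events. The third rule then only adds two grade 2 exceptions, and the fourth releases the remaining grade 2 events. This is plausible and probably what was meant. It requires, however, that the ALT/AST bracket be only an example, while the parallel bracket after myopathy is plainly a definition. The counter-reading shows that the text is ambiguous; it does not show that the outcome is stated.

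It can also be said that the literal reading proves too much, because other grade 3–4 liver events without a transaminase rise would be restarted as well. That is true, and the edits below do not address those events. For them there is no reversal by severity, however, since the other grade 2 hepatotoxicities may be restarted too.

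On practical risk the objection largely stands:

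- Section 6.2 lists neither event as a risk of the agent.
- Harm needs a related grade 3–4 event, no related transaminase rise, resolution within six months of dosing, and then an actual restart.
- An event that is life-threatening or needs admission is serious (11.2.1). It is phoned to the medical monitor within 24 hours and reported in writing within 48 hours (11.2.2), followed until resolved if related (11.2.3), and reviewed at the data monitoring committee's bi-weekly meetings (12.4).
- An investigator may keep the participant off agent under Section 8.3.

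These safeguards make unsupervised re-exposure unlikely. They do not tell a site which outcome the protocol requires.

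Finally, the exception clause in the restart sentence may look unnecessary, because specific text ordinarily governs general text. That is fair as a rule of reading, but the restart sentence is unqualified and mandatory, and the clause removes its surface conflict with the permanent rules that follow.

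**Conclusion.** The concern holds as a minor point. Followed as written, Section 5.6 permanently stops the agent for the two named events at grade 2 and restarts it after the same events at grade 3–4 when related ALT/AST above 5 times ULN is absent. This is most likely a drafting gap, not a deliberately laxer policy.

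The conclusion rests on the literal text, with the ALT/AST bracket read as a definition, and on the published document alone; the separate Data and Safety Monitoring Plan mentioned in Section 12.4 is not part of it. Sample size, power, endpoints and analyses are unaffected.

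**What to change.** Make two edits, both in Section 5.6:

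1. Open the restart sentence with *Except where permanent discontinuation is required below*.
2. In the hemorrhage and fistula rule, change *grade 2* to *grade 2 or greater*.

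Leave the list of two events, the sentence on other grade 2 hepatotoxicities, and the myopathy and ALT/AST rules as they are.

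The first edit adds 7 words and the second adds 2, so 7 + 2 = 9 words added and none deleted. They need a protocol amendment and can travel with the next one. No visit, procedure or data item is added, and the grade 2 rule is not broadened.

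The cost is that, rarely, one more participant stops the agent for good. Such a participant stays in the study where feasible, under Section 8.3: "Participants will continue to be followed, if possible, for safety reasons and in order to collect endpoint data". Section 13.5 analyses all participants as randomized.

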2.2 Study Agent

[figure not shown]

Figure 1. Molecular structure of simvastatin

Simvastatin (butanoic acid, see Figure 1) is a lipid-lowering agent that is derived synthetically from a fermentation product of *Aspergillus terreus*. After oral ingestion, simvastatin, which is an inactive lactone, is hydrolyzed to the corresponding β -hydroxyacid form. This is an inhibitor of 3-hydroxy-3-methylglutaryl-coenzyme A (HMG-CoA) reductase. This enzyme catalyzes the conversion of HMG-CoA to mevalonate, an early and rate-limiting step in the biosynthesis of cholesterol. The empirical formula of simvastatin is C₂₅H₃₈O₅ and its molecular weight is 418.57. Simvastatin is a white to off-white, nonhygroscopic, crystalline powder that is practically insoluble in water, and freely soluble in chloroform, methanol, and ethanol.

Simvastatin tablets for oral administration contain 5 mg, 10 mg, 20 mg, 40 mg, or 80 mg simvastatin and the following inactive ingredients: ascorbic acid, citric acid, hydroxypropyl cellulose, hypromellose, iron oxides, lactose, magnesium stearate, microcrystalline cellulose, starch, talc, and titanium dioxide. Butylated hydroxyanisole is added as a preservative.

Simvastatin is the most commonly prescribed HMG-CoA reductase inhibitor, which has a widely accepted tolerability profile with few serious side effects [21]. Potential, but uncommon side effects include muscle, liver, and kidney problems. Elevated levels of creatine kinase and rhabdomyolysis occur in <1% of consumers, and myalgia, or muscle ache or weakness, can occur in approximately 5% of consumers [22]. In a clinical trial database in which 41,413 patients were treated with simvastatin, 60% of whom were enrolled in studies with a median follow-up of at least 4 years, the incidence of myopathy was approximately 0.03% and 0.08% at 20 and 40 mg/day, respectively. The incidence of myopathy with 80 mg (0.61%) was disproportionately higher than that observed at the lower doses [23].

Simvastatin is prescribed for primary and secondary prevention of cardiovascular disease and thus is indicated for long-term use. We propose to administer simvastatin 40 mg daily for 6 months in this trial.

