6.2 Reported Adverse Events and Potential Risks

The most common reported adverse events (incidence $\geq 5.0\%$) are upper respiratory infection, headache, abdominal pain, constipation, and nausea. Other adverse events reported in clinical trials (<5%) were diarrhea, rash, dyspepsia, flatulence, and asthenia.

Persistent increases in serum transaminases (to more than $3 \times$ the ULN) have occurred in approximately 1% of patients who received simvastatin in clinical studies. When drug treatment was interrupted or discontinued in these patients, the transaminase levels usually fell slowly to pretreatment levels. The increases were not associated with jaundice or other clinical signs or symptoms. It is recommended that liver function tests be performed before the initiation of treatment, and thereafter when clinically indicated.

Simvastatin occasionally causes myopathy manifested as muscle pain, tenderness, or weakness with creatine kinase above ten times the ULN. Myopathy sometimes takes the form of rhabdomyolysis with or without acute renal failure secondary to myoglobinuria, and rare fatalities have occurred. The risk of myopathy is increased by high levels of statin activity in plasma. Predisposing factors for myopathy include advanced age (≥65 years), female gender, uncontrolled hypothyroidism, and renal impairment. The risk of myopathy, including rhabdomyolysis, is dose related. The risk of myopathy and rhabdomyolysis is increased by high levels of statin activity in plasma. Simvastatin is metabolized by the cytochrome P450 isoform 3A4 (CYP3A4). Certain drugs which inhibit this metabolic pathway can raise the plasma levels of simvastatin and may increase the risk of myopathy. These include itraconazole, ketoconazole, posaconazole, voriconazole, the macrolide antibiotics erythromycin and clarithromycin, the ketolide antibiotic telithromycin, HIV protease inhibitors, boceprevir, telaprevir, the antidepressant nefazodone, cobicistat-containing products, or grapefruit-containing products. Combination of these drugs with simvastatin is contraindicated. If short-term treatment with strong CYP3A4 inhibitors is unavoidable, therapy with simvastatin must be suspended during the course of treatment.

Increases in HbA1c and fasting serum glucose levels have been reported with HMG-CoA reductase inhibitors, including simvastatin.

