The CMPL and CBDF test results will be utilized to screen for any issues that could be related to an adverse event or affect eligibility for continuation in the trial. It is the consensus of the liver expert panel that obtaining baseline liver enzymes (AST/ALT) and monitoring them is optimal in the care of statin-treated patients [115]. CBDF and CMPL lab results from the Screen 1 eligibility visit (blood collected at most 30 days prior to Study Visit 1) will be used to establish patient-specific references prior to initiation of therapy. If blood tests were not done at the Screen 1 visit for a CBDF and CMPL; and lab results within 30 days prior to Study Visit 1 for these tests are not available in the medical record, a CBDF and CMPL will be done at Study Visit 1. The Lipid Panel includes tests for cholesterol, high density lipoprotein cholesterol, low density lipoprotein cholesterol, and triglycerides. Since the study agent is a cholesterol lowering agent, we feel that it is important to establish baseline lipid levels prior to initiating the study agent (Study Visit 1) and monitor lipids at Study Visits 3 and 4 (3- and 6-month visits). Hemoglobin A1C is used to assess glucose control in insulin-dependent diabetics whose glucose levels are very labile and in whom single blood glucose measurements may not accurately reflect the level of control present over the preceding few weeks. Glucose and hemoglobin A1C will be used for monitoring adverse events (incident diabetes) during the trial. CPK will be tested to establish a baseline for

monitoring myopathy, a rare complication associated with the study agent (<1%). We will measure levels of CPK at Study Visit 1 to establish a patient-specific reference for this indicator of muscle toxicity. If the participant reports unexplained muscle pain or weakness during the trial, CPK will be tested again to check for elevation.

An additional blood specimen (20 mL) will be collected from each participant at Study Visits 1 and 4 for research purposes. The blood will be drawn into one 10 mL red top serum vacutainer tube for measurement of protocol-specific biomarkers (AFP, AFP-L3%, IL-6, deoxycholic acid, and other serum bile acids and immune markers), and one 10 mL lavender top EDTA tube for DNA extraction and use in future studies.

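### Section 5.6 makes restart at 40 mg the written default after a related grade 3 or greater muscle event with CPK at or below 5 times ULN, and Section 8.3 does not say that it overrides this

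*Combined protocol and SAP*

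**What the plan says.** Section 5.6 (Dose Modification) opens with "No dose modifications are planned". It stops the agent for any adverse event of grade 3 or greater judged at least possibly related, and adds: "The study agent will be restarted after resolution". The sentence does not mention investigator judgement.

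The same section separates myalgia, which it describes as muscle pain with normal CPK, from "statin myopathy (muscle weakness or other muscle injury with or without elevation in CPK level"). Its permanent-stop rule for muscle events is narrower: "The study agent will be permanently discontinued in subjects experiencing grade 3 or greater myopathy (unexplained muscle symptoms" together with CPK above 5 times ULN). The other permanent stops are for liver enzymes above 5 times ULN and two named grade 2 events. For the remaining grade 2 hepatotoxicities, 5.6 permits restart but does not direct it.

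Section 5.1 gives a single regimen, one 40 mg capsule (or placebo) daily. Section 8.3 (Off-Agent Criteria) says participants may stop the agent for reasons that include an adverse event, a serious adverse event and a medical contraindication, and refers to 5.6 for further off-agent criteria. Section 8.4 lists physician decision among the reasons for leaving the study. Exclusion 4.2.3 bars anyone with past adverse effects or intolerance attributed to other statins.

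**The concern.** Section 5.6 accepts that statin muscle injury can occur without a raised CPK, yet its permanent-stop rule leaves those cases out. They fall back on the general restart sentence, which is worded as an instruction. Restart after a grade 3 or greater event is thus directed more firmly than restart after most grade 2 liver events, where it is only allowed.

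A site that follows 5.6 to the letter would re-expose a participant to the full dose after a severe, drug-related muscle event once it had resolved. A comparable history on another statin would have barred that person from entry under 4.2.3. There are four sites, and each would have to work out from 8.3 whether it may decline. A site that declined could be seen as departing from 5.6. What is at stake is the safety of individual participants, not the validity of the primary comparison.

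**Working it through.** **Rule trace.** Take a muscle event of grade 3 or greater, judged at least possibly related.

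| Step | CPK above 5 × ULN | CPK at or below 5 × ULN |
|---|---|---|
| General stop (5.6) | Stop | Stop |
| Muscle permanent-stop rule (5.6) | Met | Not met |
| Other permanent-stop rules (5.6) | Not needed | Not met by a muscle event alone |
| Written outcome in 5.6 | Permanent discontinuation | Restart after resolution |
| Dose at restart | – | 40 mg (or placebo), inferred |

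The restart sentence names no dose. The 40 mg is inferred from the absence of planned dose modification (5.6) and the single regimen (5.1).

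**Does another section change the right-hand column?** Section 8.3 deals with stopping and treats the 5.6 criteria as additions to its own list. It does not mention restart or say which section prevails. Section 8.4 concerns leaving the study, which is a different decision from staying off agent. Section 6.2 describes "myopathy manifested as muscle pain, tenderness, or weakness with creatine kinase above ten times the ULN" but gives no restart rule for lower values. The restart instruction therefore stands beside a general discretion, and the two are not reconciled.

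**How many participants?** The simvastatin arm has 40.

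- Myalgia, muscle ache or weakness, any grade, about 5% (Section 2.2): 40 × 0.05 = 2 participants.
- Myopathy, below 1% (Section 5.6, tied to myopathy in Section 7.6): fewer than 40 × 0.01 = 0.4 participants.
- Trial-database rate in Section 2.2: "the incidence of myopathy was approximately 0.03% and 0.08% at 20 and 40 mg/day, respectively". At 40 mg this gives 40 × 0.0008 = 0.032 participants.

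None of these is the rate needed. The first covers all grades. The second leaves out normal-CPK myalgia, which falls into the gap if severe. The third may count only cases with very high creatine kinase, given the description in 6.2. The documents give no rate for related grade 3 or greater muscle events with CPK at or below 5 times ULN, and no rate specific to cirrhosis.

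**Cost of not restarting, in power.** Inputs from Section 13.4 and Table 2: 36 per arm, one-sided alpha 0.10, expected change 2.8, SD 5.3, Wilcoxon-Mann-Whitney test, stated power 0.81. A normal-data approximation with efficiency 3/π is

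power ≈ Φ( √(3/π) × d / (5.3 × √(2/36)) − 1.2816 )

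- Plan's case, d = 2.80: 5.3 × √(2/36) = 1.249; 0.977 × 2.80 / 1.249 = 2.190; Φ(2.190 − 1.2816) = 0.818, close to the stated 0.81.
- One simvastatin patient with no effect at all: d = 2.8 × 35/36 = 2.72; 0.977 × 2.72 / 1.249 = 2.129; Φ(2.129 − 1.2816) = 0.802.

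The loss per patient is thus at most about 0.08 in the expected change and about 0.016 in power.

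**The case against.** The strongest reply is that 8.3 already settles the matter. It lists adverse events and medical contraindication as reasons to stop, treats 5.6 as supplementary, and provides for participants who discontinue permanently without limiting them to the 5.6 criteria. On that reading 5.6 adds mandatory stops to a general discretion. Other safeguards exist too: CPK is retested when unexplained muscle symptoms are reported, calls every four weeks ask about muscle aches, adverse events are followed according to good medical practice (11.1.5), and participants may withdraw at any time. Much of this stands. A reader might infer that the protocol compels re-exposure, and the documents do not support that: restart is a default, it applies only after resolution, and 8.3 offers a way out. What 8.3 does not do is qualify an instruction specific to restart.

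A second reply is that the CPK threshold is a deliberate choice between confirmed muscle injury and symptoms alone. That also stands. A reader might infer that the threshold is wrong or that low-CPK events should be a mandatory stop, but nothing in the documents shows that rechallenge after resolution is unsafe in such cases.

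A third reply is that the event is too rare to matter. A reader might take the below-1% figure as a ceiling, giving fewer than 0.4 of 40 patients and at most a 1 − 0.99^40 = 33% chance of any case. That is not supported, because the gap also catches severe myalgia with normal CPK, which the myopathy figure does not cover.

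**Conclusion.** The point holds as a gap in safety wording. For a related grade 3 or greater muscle event with CPK at or below 5 times ULN, the written default in 5.6 is restart at 40 mg without stated judgement, and no section says that the discretion in 8.3 prevails. The event should be uncommon, but the documents do not allow it to be sized: about 2 of 40 may have muscle symptoms of any grade, and the severe, related, low-CPK share is unknown. The conclusion rests on reading 5.6 literally and on the inferred restart dose. Consent pages were not available, so any stopping language there could not be considered. The priority is low: consider at the next amendment.

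**What to change.** In Section 5.6, replace the restart sentence with:

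> The study agent may be restarted after resolution at the investigator's discretion, unless a permanent-discontinuation criterion below is met. This discretion applies to related grade 3 or greater muscle events with CPK at or below 5 times ULN. Participants not restarted are followed off agent under Section 8.3.

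Leave the trigger of CPK above 5 times ULN unchanged. The second sentence is worded as a discretion so that it cannot be read as a new mandatory stop. The change also makes restart discretionary for every other related adverse event of grade 3 or greater that meets no permanent-stop criterion, which should be a conscious decision.

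The editorial cost is three sentences in place of one. Section 8.3 already provides for follow-up and endpoint collection off agent where possible, and Section 13.5 specifies intention-to-treat analysis, so no new procedure or analysis is needed. The statistical cost is the small dilution shown above, and only for participants in the simvastatin arm who would otherwise have gone back on the drug. The endpoints, the alpha and the study stopping rule in Section 8.5 stay as they are.
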